#### **Adherence**

Adherence will be displayed for the CP by genotype and cirrhosis status and for the SP by treatment regimen and cirrhosis status. Summary statistics (n, mean, median, standard deviation [SD], and range) will be generated for continuous variable. Numbers and percentages of patients will be presented for categorical variables.

- Adherence to Abbvie regimen (% of target dose [adherence=cumulated number of pills taken /(initial prescribed number of pills x planned duration)])
  - o **>105%**
  - >95%-<=105%

  - o >80%-<=95%
  - o >50%-<=80%
  - o <=50%
- Adherence to ribavirin (% of target dose [adherence=cumulated dose taken /(initial prescribed dose x planned duration)])

- o >105%
- o >95%-<=105%
- o >80%-<=95%
- o >50%-<=80%
- o <=50%
- Percentage of actual treatment duration in relation to the target duration of ABBVIE regimen taken
- Deviating duration of ABBVIE regimen
  - o Early discontinuation (actual duration is shortened for more than 7 days)
  - Not deviated
  - Exceedance (actual duration is prolonged for more than 7 days)
- Method used to document adherence (Interview, Diary)
- Percentage of actual days with treatment with RBV in relation to the planned duration
- Ribavirin earlier discontinued than ABBVIE regimen
- Initial dose of Ribavirin
  - o 1000 mg/day
  - o 1200 mg/day
  - o XXX
- Cumulative dose of Ribavirin (g)
- Dose modifications/termination of RBV [in patients taking RBV, for a patient more than
  one dose modification and its main reason could be reported, but for each single reason
  the patient is counted only once] (Total number of patients with lower dose than highest
  previous dose [including patients who stopped the treatment earlier], Anemia,
  Nausea/Vomiting, Rash, Other [including patients who discontinued ABBVIE regimen
  earlier, but did not stop the RBV treatment before the ABBVIE regimen])

In addition to the summary statistics of the adherence variables, logistic regression analyses will be performed for the following adherence variables: "adherence to Abbvie regimen" in all patients of the CP, "adherence to ribavirin" in all patients of the CP taking RBV, each categorized as follows: >=95%, >80%-<=95%, <=80% to investigate the additional impact of overall treatment adherence on SVR24. The categories may be changed if they are sparsely filled. Adherence will be included as mandatory covariate in addition to the baseline explanatory variables already mentioned above. Also the same methods will be applied as described above.

An overview of Tables is given in Table 8.

Table 8 Overview of Outputs for Primary and Secondary Effectiveness Analysis

Output Title	Output Short Name	Analysis Population
Virological Response Rates by Genotype and Cirrhosis Status – CP/CPSFU - <country></country>	tvr_ <c>_gc_cp</c>	Core population/ Core population with sufficient follow-up data
Virological Response Rates by Genotype and Cirrhosis Status in Patients who Completed ABBVIE Regimen – CP/CPSFU - <country></country>	tvr_ <c>_gc_cp_ARC</c>	Core population/ Core population with sufficient follow-up data: patients who completed ABBVIE regimen
Virological Response Rates - NCP - <country></country>	tvr_ <c>_ncp</c>	Non-core population
Relapse Rates by Genotype and Cirrhosis Status – CP - <country></country>	trr_ <c>_gc_cp</c>	Core population
Viral Breakthrough by Genotype and Cirrhosis Status – CP - <country></country>	tvb_ <c>_gc_cp</c>	Core population
Non-Response Rates by Genotype and Cirrhosis Status – CP - <country></country>	tnrr_ <c>_gc_cp</c>	Core population
Non-Response Rates by Genotype and Cirrhosis Status in Patients who Completed ABBVIE Regimen – CP - <country></country>	tnrr_ <c>_gc_cp_ARC</c>	Core population: patients who completed ABBVIE regimen
Impact of Patient and Disease Characteristics on SVR24 – CP - <country></country>	tis_ <c>_cp</c>	Core population
Adherence by Genotype and Cirrhosis Status - CP - < country>	tah_ <c>_gc_cp</c>	Core population
Adherence by Treatment Regimen and Cirrhosis Status - SP - <country></country>	tah_ <c>_gc_sp</c>	Safety population
Impact of Adherence to AbbVie Regimen on SVR24 - CP - <country></country>	tiaa_ <c>_cp</c>	Core population
Impact of Adherence to Ribavirin on SVR24 in patients taking RBV – CP - <country></country>	tiar_ <c>_cp_RBV</c>	Core population: patients taking RBV

The layouts of the tables mentioned above are provided in Part II of the SAP (Table Shells).

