9.3.2 Secondary Variables

- Type of treatment regimen (± Dasabuvir, ± RBV, intended and actual combination, dose and duration)
- Adherence
 - Percentage of the DAA dose taken in relation to the target dose of DAA (cumulative dose taken divided by target dose in percent)
 - Percentage of the RBV dose taken in relation to the target dose of RBV (cumulative dose taken divided by target dose in percent)

Confidential Information

- Percentage of missed RBV treatment days in relation to the target number of RBV treatment days
- Co-morbidities and concomitant medication
- Serious and non-serious adverse events and pregnancy occurrences
- Questionnaires on PROs: e.g. EuroQol 5 dimension 5 level (EQ-5D-5L) questionnaire and work productivity and activity impairment (WPAI) questionnaire prior to treatment initiation, at EoT as well as 12 and 24 weeks after EoT

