# 4.2.5 Patient Disposition

The frequencies of patients belonging to the different populations (i.e. EP, TP, CP, CPSFU; SP) will be summarized by genotype and cirrhosis status and overall using the EP analysis groups as specified in section 4.2.1. The reasons for exclusion from a particular population will be also summarized in the frequency tables. Additionally, information on patient disposition will be listed.

Furthermore the frequency of patients not completing the study as defined per protocol (i.e. no HCV RNA assessment performed at least 10 weeks post-treatment), will be summarized by treatment regimen and cirrhosis status and additionally by genotype and cirrhosis status and overall for the SP and CP. The reasons for not completing the study as entered on the CRF will be displayed (i.e. failure to return, insufficient virological response (HCV RNA detectable at End of treatment, Relapse post-treatment), patient never started treatment, withdrawn consent, death, other).

Additionally, the main reason for early termination of the ABBVIE regimen (AE or SAE [Physician decision], virological non-response [Physician decision], rebound or breakthrough [Physician decision], resistance to DAA [Physician decision], patient refused to continue treatment, patient withdrew consent to participate in the study, lost to follow-up, other, unknown [if actual duration is shortened for more than 7 days]) and Ribavirin (Anemia, Nausea/Vomiting, Rash, Other) will be summarized by treatment regimen and cirrhosis status and additionally by genotype and cirrhosis status and overall for the following different analysis populations: CP and SP.

Finally the study regimens assigned at baseline will be summarized (a) by genotype and cirrhosis status and (b) by genotype and pre-treatment status (treatment naïve vs treatment experienced) for CP and SP.

An overview of Tables is given in Table 6.

Table 6 Overview of Outputs for Patient Disposition

Output Title	Output Short Name	Analysis Population
Patient Disposition by Genotype and Cirrhosis Status – EP - <country></country>	tdis_ <c>_gc_ep</c>	Patients Enrolled
Listing of Patient Disposition - EP- <country></country>	ldis_ <c>_ep</c>	Patients Enrolled
Premature Termination of the Study and its Main Reason by <treatment genotype="" regimen=""> and Cirrhosis Status - CP - <country></country></treatment>	tps_ <c>_<t g="">c _cp</t></c>	Core population

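### The RBV adherence regression uses dose received against the initial target, so it cannot separate missed doses from dose modification, and two of its classes both contain 95%

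*SAP*

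**What the plan says.** Protocol 9.3.2 lists the variable as "Percentage of the RBV dose taken in relation to the target dose of RBV (cumulative dose taken divided by target dose in percent", and does not say whether the target follows later changes in the prescribed dose. It lists missed RBV treatment days as a separate item.

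The Adherence part of SAP 4.2.7.2.1 settles the denominator: "adherence=cumulated dose taken /(initial prescribed dose x planned duration". The same list tabulates days on RBV against the planned duration, RBV stopped before the AbbVie regimen, initial dose, cumulative dose, and a dose-modification row that starts "Total number of patients with lower dose than highest" (the comparison is with the earlier dose). Reasons for modification are anemia, nausea/vomiting, rash and other. SAP 4.2.5 gives the same reasons for early termination: "Ribavirin (Anemia, Nausea/Vomiting, Rash, Other) will be summarized by treatment regimen and cirrhosis status".

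For the regressions on SVR24 the SAP takes only the AbbVie-regimen ratio (all CP patients) and the RBV ratio (CP patients taking RBV), "each categorized as follows: >=95%, >80%-<=95%, <=80" (percent). It adds: "Adherence will be included as mandatory covariate in addition to the baseline explanatory variables already mentioned above". The only flexibility is: "The categories may be changed if they are sparsely filled".

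**The concern.** Objective 4 is the influence of adherence on treatment outcome. A shortfall in the RBV ratio can arise because the patient skipped doses, or because the prescribed dose was lowered or RBV was stopped. These have different causes and may relate differently to response. The plan expects modifications, since it tabulates them with toxicity reasons, but the regression does not use that information. A coefficient reported as an adherence effect would then partly describe tolerability and dose intensity. A physician reading it as evidence on compliance would be misled.

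The second matter is a specification slip. A value of 95% meets the definition of two regression classes, so the derived variable is not uniquely defined there.

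**Working it through.** The plan states no figure to reproduce here. The point rests on a definition and on class limits.

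**Inputs**
- Ratio and class limits: SAP 4.2.7.2.1, Adherence.
- Starting doses of 1000 and 1200 mg/day: named as categories in the same list.
- Courses of 12 weeks (84 days) and 24 weeks: SAP 3.1.
- Size and timing of reductions: assumed. Neither document gives any. They serve the arithmetic only and are not a clinical rule.

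**Formula.** Take a patient who takes every prescribed dose. If the daily dose D is cut by a fraction r after week w of W, the dose taken is proportional to w + (1 − r)(W − w), so the SAP ratio is A = 1 − r(1 − w/W). If the daily dose is lower by d mg for n days of 84, A = 1 − n·d/(84·D).

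| Case (no dose missed) | Calculation | A | Regression class |
|---|---|---|---|
| 1200 mg/day, 200 mg lower for 25 days | 1 − 5,000/100,800 | 95.04% | top |
| 1200 mg/day, 200 mg lower for 26 days | 1 − 5,200/100,800 | 94.8% | middle |
| 1000 mg/day, 200 mg lower for 21 days | 1 − 4,200/84,000 | 95.0% | top and middle |
| Halved for 34 days of 84 | 1 − 0.5 × 34/84 | 79.8% | lowest |
| Halved from day 29 of 84 | (28 + 0.5 × 56)/84 | 66.7% | lowest |
| 20% cut after week 4 of 12 | 1 − 0.20 × 8/12 | 86.7% | middle |
| 25% cut after week 4 of 24 | 1 − 0.25 × 20/24 | 79.2% | lowest |

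For cuts of 20, 25, 40 and 50% after week 2, 4 or 8 of either course, A runs from 1 − 0.5 × 22/24 = 54.2% to 1 − 0.2 × 4/12 = 93.3%. None reaches the top class. Dose taken over dose prescribed is 100% in every case.

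**Why the model cannot separate the causes.** A patient on an unchanged dose who skips 28 of 84 days scores 56/84 = 66.7%, the same as the fully compliant patient whose dose was halved from day 29. The share of planned days on RBV is 66.7% for the first and 84/84 = 100% for the second. The planned days measure separates them, but it is not in the regression.

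**Class limits.** 95% satisfies both the top class (at least 95%) and the middle class (above 80%, up to and including 95%). 80% satisfies only the lowest. The summary classes in the same section (above 95% to 105%, above 80% to 95%) do not overlap.

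**Events available.** At the planning figures (Protocol 9.5: 360–380 evaluable patients, SVR12 of 90–95%), expected failures in the whole CP are between 360 × 5% = 18 and 380 × 10% = 38. Carrying these SVR12 rates over to SVR24 is an assumption. The RBV subset can contain no more failures than the whole CP.

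**The case against.** The SAP labels its ratio as a percentage of target dose, which fits the protocol's wording. Share of the planned course received is a legitimate quantity, and choosing between it and compliance with current orders is a choice of estimand. Taken over prescribed has its own weakness: a patient whose RBV is stopped very early on medical advice would score 100%. The models are exploratory, and no primary result depends on them. All of this stands. It argues for keeping the ratio under a clear name, not for reading its coefficient as adherence.

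Some stronger readings are tempting, but the documents do not support them.
- A reader might infer that a patient is judged against three different references. The SAP formula makes the protocol's target dose operational, and the highest earlier dose is only the counting rule for the separate modification row.
- A reader might infer that the summary table overstates non-adherence to RBV. That table also shows RBV days, cumulative dose and modifications with reasons, and no class is labelled non-adherent.
- A reader might call it an error that values above 105% fall into the top regression class. That is ordinary collapsing of sparse classes.
- A reader might ask for a model term for reductions ordered by the physician. The listed reasons do not say who decided, and the 'other' category includes patients who stopped the AbbVie regimen early, so such a term may not be derivable.

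**Conclusion.** The concern holds for the RBV regression. As specified, its coefficient combines missed doses with dose modification for toxicity, so it does not answer objective 4 as an adherence effect. The class change is arithmetic and certain for any patient with a long enough or deep enough reduction. The examples range from 54.2% to 95.04%, depending on assumed reductions. How many patients are affected, and in which direction the coefficient moves, cannot be determined, because the documents give neither the frequency nor the size of reductions.

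The overlap at 95% is a real but small error. It affects only values of exactly 95%, or rounded to it, and it applies to both adherence variables. Permission to change sparsely filled categories does not resolve it. Neither matter touches the primary SVR12 estimate.

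**What to change.** 1. Keep the existing ratio, but label and interpret it as RBV dose received relative to the initial target (dose intensity), including in the title of the regression output in SAP Table 8.
2. In the RBV regression, either add a yes/no term for a recorded RBV dose modification, or repeat the model with the already planned percentage of RBV treatment days as the adherence variable. If the eCRF holds dated dose levels, dose taken over dose prescribed is a further choice; the documents do not show that it does.
3. State the limits of the chosen route. The yes/no term separates the causes only in part, because among modified patients the ratio still reflects the depth and length of the change. The days measure is unaffected by a lower daily dose but still counts an ordered early stop as a shortfall.
4. For both adherence variables, use the classes >95%, >80%–<=95% and <=80%, which match the summary table's limits at 95% and 80%.

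The cost is SAP wording plus one more term or one sensitivity run. The extra term is not free: the model already offers more than 20 candidate covariates against roughly 18 to 38 expected failures at the planning rates, so the repeat with RBV days may be the easier route. No dose or clinical rule is proposed.

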#### **SVR24 (Exploratory Analyses)**

Univariate and multiple logistic regression (MLR) methods will be used to investigate the impact of various explanatory covariates (patient and disease characteristics) at baseline on SVR24.

These analyses will be of exploratory nature, data driven, and will be performed for CP population. Univariate logistic regression will be performed first and then backward selection procedures will be applied to generate the final MLR model. A p-value <0.05 will be used for the covariates to stay in the model in a backward elimination step. If the percentage of patients with available data for a variable is lower than 80% of the patient group analyzed, then this variable will not be considered in the MLR analysis.

The variables to be considered are as follows:

- · Key demographic information
  - o Age (continuous)
  - o Gender (Female [reference], Male)
  - Race/ethnic origin (White/Caucasian [reference], Black, Asian/Oriental, Other [all other races]); at least two categories with at least 10% of the patients each have to exists, so that this variable will be considered
  - Weight (continuous)
  - o BMI (continuous)
  - IL28B, rs12979860 (CC [reference], CT or TT); patients with unknown genotype are excluded from the respective analyses.
- CHC disease characteristics
  - Years since diagnosis (continuous)
  - Mode of CHC infection (Drug use [reference], Other [all other answers excluding unknown], unknown);
  - Most recent stage of liver fibrosis (No cirrhosis/Transition to cirrhosis [reference],
     Cirrhosis; for definition see 4.2.6.2);
- HCV RNA level at baseline (log10 IU/mL)
- HCV genotype( G1a\*, G1b, G4; for definition see section 4.2.6.2)
- Type of treating institute (Private Practice / Private Hospital, Academic / University Hospital, General Hospital, Other)
- Co-infections (every patient not reporting the respective co-infection is considered as not having the respective co-infection)
  - o HIV(No [reference], Yes)
  - HBV(No [reference], Yes)
- Liver and/or CHC related co-morbidities (every patient not reporting the respective co-morbidity is considered as not having the respective co-morbidity)
  - o Liver transplantation (No [reference], Yes)
  - Steatosis (non-alcoholic) (No [reference], Yes)
  - o Decompensated liver disease (No [reference], Yes)
- Other co-morbidities (every patient not reporting the respective co-morbidity is considered as not having the respective co-morbidity)

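### The exploratory ribavirin-adherence model for SVR24 has no term for DAA adherence or completion, so early stops of the whole regimen pull the ribavirin odds ratio below 1

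*SAP*

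**What the plan says.** Section 4.2.7.2.1 of the SAP, under Adherence, defines two ratios with the same structure:

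- DAAs: "Adherence to Abbvie regimen (% of target dose [adherence=cumulated number of pills taken /(initial prescribed number of pills x planned duration".
- Ribavirin: "Adherence to ribavirin (% of target dose [adherence=cumulated dose taken /(initial prescribed dose x planned duration".

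Both denominators use planned, not actual, duration.

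Two regressions on SVR24 follow, one per ratio. The DAA model uses all core-population (CP) patients. The ribavirin model is fitted "in all patients of the CP taking RBV, each categorized as follows: >=95%, >80%-<=95%, <=80" per cent. On the terms of these models the SAP says: "Adherence will be included as mandatory covariate in addition to the baseline explanatory variables already mentioned above". The list referred to is under SVR24 (Exploratory Analyses) and concerns the "impact of various explanatory covariates (patient and disease characteristics) at baseline on SVR24". It holds patient, disease, co-morbidity, laboratory and site-type variables, and no measure of DAA adherence, actual duration or early discontinuation.

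Table 8 gives each model its own output: "Impact of Adherence to AbbVie Regimen on SVR24" and "Impact of Adherence to Ribavirin on SVR24 in patients taking RBV".

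The item "Ribavirin earlier discontinued than ABBVIE regimen" is in the descriptive adherence summary but is not named as a model term. Under SAP 4.2.3, a patient whose SVR24 value is still missing after the imputation steps counts as a failure.

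**The concern.** Low ribavirin adherence can arise in two ways. A patient may reduce or stop ribavirin and finish the DAAs, or may stop everything. Only the first tells us about ribavirin. The ratio scores both as ribavirin not taken, and nothing in the model tells them apart. Lost DAA exposure can then appear as an association with ribavirin.

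Loss to follow-up adds to this. The SAP lists it among the reasons for early termination of the regimen (4.2.5), and the regressions run in the CP, where unresolved missing SVR24 is a failure. One event can therefore produce both low ribavirin adherence and a failed outcome.

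At stake is the reading of one secondary output under objective 4, the influence of adherence on outcome. A reader of a table titled as the impact of ribavirin adherence could conclude that reducing ribavirin costs response when the data show only that abandoning treatment does.

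**Working it through.** **The plan's own figure.** None is given for this regression. The only sizing figure is the SVR12 confidence-interval width (SAP 3.2). For 324/360 the exact limits are 86.4 to 92.9, width 6.47, which agrees with the stated 6.5%. It does not bear on this point.

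**Step 1: where a whole-regimen stop lands.** With full doses until a stop on day d of T planned days, both ratios equal d/T.

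- 12 weeks (T = 84): day 28 gives 33.3%, day 56 gives 66.7%, day 67 gives 79.8%. Since 0.80 × 84 = 67.2, every stop by day 67 is in the lowest class. Since 0.95 × 84 = 79.8, days 68 to 79 are in the middle class.
- 24 weeks (T = 168): 0.80 × 168 = 134.4 and 0.95 × 168 = 159.6. Stops by day 134 are in the lowest class and days 135 to 159 in the middle class.

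This step needs no assumption beyond full dosing up to the stop.

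**Step 2: direction.** Let r be the share of ribavirin patients with a ribavirin-only reduction to 80% or less, s the share stopping everything early enough to be in that class, p the SVR24 rate in DAA completers and q the rate in stoppers. Suppose ribavirin intake has no effect of its own. Then

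SVR24 in the lowest class = (r·p + s·q)/(r + s),

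which is below p whenever s > 0 and q < p. The odds ratio against patients above 80% is therefore below 1.

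**Step 3: size, on assumed inputs.** The documents do not give r, s, q or the number taking ribavirin. Assume p = 96% (odds 24), r = 5-15%, s = 2-4%, q = 40-70%.

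| r | s | q | SVR24, lowest class | Odds ratio (true 1) |
|---|---|---|---|---|
| 5% | 4% | 40% | (0.048 + 0.016)/0.09 = 71.1% | 2.46/24 = 0.10 |
| 10% | 4% | 40% | (0.096 + 0.016)/0.14 = 80.0% | 4.00/24 = 0.17 |
| 15% | 2% | 70% | (0.144 + 0.014)/0.17 = 92.9% | 13.17/24 = 0.55 |

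The first and last rows are the extremes of this grid. A wider grid (s = 1-5%, r = 5-20%, q = 30-70%) gives 0.07 to 0.75. With r = 0 the lowest class holds stoppers only; q = 50% then gives 1/24 = 0.04, and no model can separate the two effects.

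**Step 4: effect of a DAA term, and its price.** In simulations of the first grid with 150 and 250 ribavirin patients (Firth logistic regression, Wald test, adherence split at 80%, no baseline covariates), a nominal 5% test of ribavirin rejected in about 14-93% of studies without the DAA term and 2-7% with it. With the term, the median ratio of upper to lower 95% limit for the ribavirin odds ratio was about 33 to 540.

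A hand calculation shows why. Take 200 ribavirin patients, r = 10%, s = 4%. Among completers there are 20 with ribavirin reduced (0.8 expected failures, 19.2 successes) and 172 without (6.88 and 165.12). The standard error of the log odds ratio is √(1/0.8 + 1/19.2 + 1/6.88 + 1/165.12) = 1.21, so upper/lower = exp(2 × 1.96 × 1.2056) ≈ 113.

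**The case against.** The strongest reply is that the SAP never promises a ribavirin effect net of DAA exposure. Objective 4 asks about adherence in general, and the Adherence text speaks of overall treatment adherence. As a description of how total ribavirin intake relates to response, the model does what it says. That stands, and it is why labelling is part of the remedy. It does not remove the problem, because the output carries ribavirin's name and sits beside a separate DAA output, which invites a drug-specific reading.

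The stakes are also low. The analyses are declared exploratory and data driven, they lie outside the primary analysis and the sizing, and protocol 9.9 already names uncontrolled confounding as a limitation. This stands too.

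Thirdly, the SAP tabulates early discontinuation, actual duration and earlier ribavirin discontinuation, and repeats the response tables in regimen completers. These help a careful reader, but none cross-classifies ribavirin adherence with DAA completion.

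A reader might infer from the simulated rejection rates that the planned model will probably report a false ribavirin effect. The documents do not support that. The rates rest on invented frequencies and a two-class simplification. The SAP has three classes that may be merged if sparse, and a long covariate list with backward elimination, which was not simulated. The only nearby statement in the documents is a low discontinuation rate in Phase III (protocol 7.1).

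**Conclusion.** The concern holds as a matter of structure and direction. The ribavirin model has no DAA-adherence or completion term, and its adherence measure counts planned days after a whole-regimen stop as ribavirin not taken. The odds ratio is therefore biased below 1 if such patients fail more often or are lost and counted as failures.

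Confidence is high for the direction under that condition and low for the size. The range of about 0.1 to 0.55 against a true 1 is illustrative and depends wholly on the assumed stop rate, ribavirin-only reduction rate and response in stoppers. Nothing here touches the primary SVR12 estimate. It is a cheap improvement to an exploratory analysis.

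**What to change.** In SAP 4.2.7.2.1, Adherence:

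1. Fit the ribavirin-adherence model in CP patients taking ribavirin who completed the ABBVIE regimen, using the SAP's existing rule of not more than 7 days shortened. Adding adherence to the ABBVIE regimen as a second mandatory covariate serves the same purpose.
2. Report beside it the SVR24 counts by ribavirin-adherence class and ABBVIE-regimen completion.
3. If the model without the DAA term is kept, label it as the association with overall ribavirin intake, not as a ribavirin-specific effect.
4. State in advance that if few patients reduced ribavirin only, the report will say that the two effects cannot be separated.

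The variables and the completer subset are already derived, so the cost is SAP wording, one model and one small table. The real price is precision. With few failures the ribavirin interval will be very wide, and the estimate may be uninformative. The counts in item 2 are then the more useful result.
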